### 7.2.3 Secondary endpoint analyses

#### ZAN-BPD response

The secondary endpoint of ZAN-BPD response (defined as  $\geq 30\%$  ZAN-BPD reduction from baseline at Week 10) is a binary endpoint. This endpoint will be analyzed through a logistic regression model to obtain an estimate of the population odds ratio and associated CIs

between BI 1358894 and placebo. This statistical model may be adjusted for factors that may influence response to treatment for BoPD, such as baseline ZAN-BPD total score ( $\leq 18$  vs  $\geq 19$ ), stable concomitant psychotherapy (yes/no), and sex (male/female).

#### DERS-16

The secondary endpoint of change from baseline in DERS-16 total score at Week 10, will be analyzed by a MMRM model similar to that of the primary efficacy endpoint.

#### STAI-S

The secondary endpoint of change from baseline in STAI-S total score at Week 10, will be analyzed by a MMRM model similar to that of the primary efficacy endpoint.

#### PHQ-9

The secondary endpoint of change from baseline in PHQ-9 total score at Week 10, will be analyzed by a MMRM model similar to that of the primary efficacy endpoint.

#### PGI-S

The secondary endpoint of change from baseline in PGI-S will be summarized by treatment arm as follows. Mean change from baseline to Week 10 and standard deviation will be presented. In addition, the frequency and proportion of patients reporting each response category at baseline and at Week 10 will be displayed. To compare change in severity as assessed by the PGI-S between the BI 1358894 treatment arms and placebo, an MMRM model similar to the model described for the primary efficacy analysis will be used.

#### CGI-S

The secondary endpoint of change from baseline in CGI-S at Week 10 will be analyzed in a similar fashion as PGI-S (described above).

### 7.2.5 Safety analyses

Adverse events will be coded using the Medical Dictionary for Drug Regulatory Activities (MedDRA). Standard BI summary tables and listings will be produced. All adverse events with an onset between start of treatment and end of the period of 28 days after the last dose of trial medication, will be assigned to the on-treatment period for evaluation.

All treated patients will be included in the safety analysis. In general, safety analyses will be descriptive in nature and will be based on BI standards. No hypothesis testing is planned.

Statistical analysis and reporting of adverse events will concentrate on treatment-emergent adverse events, i.e. all adverse events occurring between start of treatment and end of the REP. Adverse events that start before first drug intake and deteriorate under treatment will also be considered as 'treatment-emergent'.

Frequency, severity, and causal relationship of adverse events will be tabulated by system organ class and preferred term after coding according to the current version of the MedDRA at database lock.

Laboratory data will be analyzed both quantitatively as well as qualitatively. The latter will be done via comparison of laboratory data to their reference ranges. Values outside the reference range as well as values defined as clinically relevant will be summarized. Treatment groups will be compared descriptively with regard to distribution parameters as well as with regard to frequency and percentage of patients with abnormal values or clinically relevant abnormal values.

Vital signs, physical examinations, or other safety-relevant data observed at screening, baseline, during the course of the trial and at the end-of-trial evaluation will be assessed with regard to possible changes compared to findings before start of treatment.

### 7.2.7 Interim Analyses

No interim analysis is planned. A Data Monitoring Committee (DMC) will review safety data during the trial as described in section [8.7](#).

### 7.3 HANDLING OF MISSING DATA

Every effort will be made to collect complete data at all visits. The primary estimand of interest is the treatment effect assuming all participants remain adherent to the assigned trial medication and trial protocol using a hypothetical approach. For the primary analysis of the primary endpoint, missing data will not be imputed. Data collected after discontinuation of trial medication will be censored for the primary analysis. The mixed effects model will handle missing data based on a likelihood method under the assumption of missing at random.

For the supplemental analysis of the primary endpoint based on a treatment policy estimand, i.e. intention to treat, all available data including data collected after treatment discontinuation or other intercurrent event will be analyzed.

Sensitivity analyses may be conducted utilizing multiple imputation techniques for the primary and supplemental analyses of the primary endpoint. Similar methods for handling missing data will be used for secondary efficacy endpoints, as applicable. With respect to

safety evaluations, it is not planned to impute missing values. More details for missing data handling will be included in the TSAP, if needed.

#### 7.4 RANDOMISATION

Participants will be randomly assigned to treatment in a 2.5:1:1:1:2 ratio as described in section [4.1.3](#). Randomization will be stratified by baseline ZAN-BPD total score ( $\leq 18$  vs.  $\geq 19$ ).

BI will arrange for the randomization and the packaging and labelling of trial medication. The randomization list will be generated using a validated system, which involves a pseudo-random number generator so that the resulting treatment will be both reproducible and non-predictable. The block size will be documented in the Clinical trial report (CTR). Access to the codes will be controlled and documented as described in section [4.1.5.1](#).

#### 7.5 DETERMINATION OF SAMPLE SIZE

Sample size is estimated assuming a maximum standardized effect size of 0.32, which is based on a mean difference between placebo and BI 1358894 of 3.0 and standard deviation of 9.5 for the primary endpoint, a one-sided alpha of 0.10, a treatment allocation ratio of 2.5:1:1:1:2 (placebo, BI 5mg, BI 25mg, BI 75mg, BI 125mg, respectively) and the pre-specified models listed in section [7.2.2.1](#). Information on the change from baseline and its standard deviation is limited since there is no BoPD approved drug. BoPD is a symptomatic and clinically heterogeneous condition and in clinical studies a high discontinuation rate has been observed. Consequently, sample size assumptions are based on expert opinion, previous BoPD research and a quetiapine pivotal trial ([R19-1108](#), [R19-1645](#), [P11-04859](#)).

For the PoC analysis of the BI 1358894 dose groups and placebo using MCPMod approach with the parameters as listed in section [7.2.2](#), a sample size of 285 (95:38:38:38:76) evaluable patients are needed to establish PoC with about 81% average power (one-sided 10% alpha level). The powers for each model shape under different assumptions are summarized in the table below.

Assuming a 20% dropout rate is considered reasonable based on unique characteristics of this population. Therefore, a total sample size of approximately 355 randomized patients are needed for this phase II trial:

- 119 patients in placebo arm
- 47 patients in each of the three lowest BI 1358894 arms
- 95 patients in the highest BI 1358894 arm

The calculations for the PoC step have been performed using DoseFinding R-package ([R15-2001](#)). The R codes for the sample size calculations as well as the analyses using the MCPMod approach will be provided in the TSAP. The family-wise type I error rate at one sided  $\alpha = 10\%$  is controlled in the sample size calculations and the analyses.

Table 7.5: 1 Power of MCPMod for each candidate set model and average power for change from baseline in ZAN-BPD at Week 10

Model	Assumption A	Assumption B	Assumption C
Maximum effect size	0.32 (Mean=3, SD=9.5)	0.35 (Mean=3.3, SD=9.5)	0.38 (Mean=3.6, SD=9.5)
Linear	81.9%	86.7%	91.6%
E max 1	81.7%	87.7%	91.6%
E max 2	75.2%	82.7%	86.6%
Sigmax	85.4%	89.1%	93.7%
Exponential	81.0%	85.8%	90.5%
Average	81.1%	86.4%	90.8%

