The primary treatment comparisons will be the contrasts between each BI 1358894 treatment arm and placebo at Week 10. Procedures to be followed if the planned analysis fails to converge will be described in the TSAP. Resulting adjusted estimates from the MMRM will then be extracted for use in the MCPMod analysis. Parameter estimation of the MMRM will be based on the residual maximum likelihood method (REML).

For the PoC testing and for the sample size calculations, the basic shape of each of the models to be tested must be predefined. The candidate models in Table 7.2.2.1: 1 were selected to cover a plausible and diverse range of dose response patterns for the trial medication. Associated graphs of each model are shown in Figure [7.2.2.1: 1](#).

Table 7.2.2.1: 1 Models for the MCPMod analysis

Model	Estimate	Rationale
E max 1	50% of the maximum effect is achieved at 25 mg	E max curve corresponds the assumed true estimate of ED 50 =25 mg.
E max 2	70% of the maximum effect is achieved at 5 mg	To cover the possibility for which 70% of the maximum effect is achieved at 5 mg. This is a scenario in which much of the effect is achieved early on with relatively low doses. The rationale behind the two E max models is to construct one (e max 1) where the dose response is achieved as expected, while the other (e max 2) accounts for the setting of which the assumed dose response is not as expected.
Sigmax	50% of the maximum effect is achieved at 25 mg, and 90% of the maximum effect is achieved at 75 mg	Another more flexible model to cover the new estimate ED 50 =25 mg
Exponential	5% of the maximum effect is achieved at 25 mg	To cover the case where the effect of drug is mainly achieved at the higher doses.
Linear	No parameter assumptions required	In the event, dose response is linear.

The models were based on the following assumptions:

- BI 1358894 dose groups 5mg, 25mg, 75mg, 125mg and
- ED50 = 25 mg \*

\* ED50 assumes dose corresponding to EC50, FST = 77nM plasma concentration in trough at 16h.

EC50: Half maximal effective concentration

EC50 of a graded dose response curve represents the concentration of a compound where 50% of its maximal effect is observed.

FST: forced swim test (in mice)

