#### MCPMod Analysis

The adjusted mean estimates of the change from baseline at Week 10 for each dose and their estimated variance-covariance matrix from the MMRM model are used in the trial analysis stage. Then, the multiple pair-wise comparison procedure will be implemented using the optimal contrast tests which control the family-wise type I error rate at one-sided  $\alpha = 0.10$ .

For the MCPMod test, the optimal contrasts corresponding to the candidate models are calculated as in the trial design stage (using the R-function optContr using weights proportional to the sample size of each dose group) and are shown in [Table 7.4.1: 1](#) below. These contrasts will be updated using the expected model means from the candidate set and the estimated variance-covariance matrix from the data. The final contrasts will be presented in the CTR.

Table 7.4.1:1 Optimal contrast coefficients

| Model              | Optimal Contrast Coefficients for Dose |        |        |        |       |
|--------------------|--|--------|--------|--------|-------|
|                    | 0                                      | 5mg    | 25mg   | 75mg   | 125mg |
| Linear             | -0.583                                 | -0.209 | -0.110 | 0.136  | 0.765 |
| E max 1 | -0.736                                 | -0.175 | 0.064  | 0.243  | 0.604 |
| E max 2 | -0.862                                 | 0.052  | 0.177  | 0.206  | 0.425 |
| Sigmax             | -0.684                                 | -0.250 | 0.032  | 0.276  | 0.627 |
| Exponential        | -0.479                                 | -0.187 | -0.161 | -0.016 | 0.842 |

Proof of concept is established if at least one dose-response model is statistically significant, i.e., the null hypothesis of a flat dose-response curve is rejected indicating a benefit of one BI 1358894 dose over placebo.

Once the significance of a dose-response signal is established, the dose-response profile and the target dose can be estimated using the model averaging method.

The selected dose-response model(s) is re-fitted to the data without any parameter assumptions to generate a set of new estimates of the model parameters from the data. The final dose-response model is obtained via the weighted model averaging of the significant models (p-value<0.10) based on Akaike Information Criterion (AIC) (the smaller the AIC value the better the model fit). The weights for each significant model ( $M_k$ ) are given by,

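### Table 7.5:1 does not give the power of the planned five-contrast MCPMod test: Emax2 is stated at 75.2% but computes to about 82%, and Exponential, stated at 81.0%, falls just under 80%

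*Protocol*

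**What the plan says.** Protocol 7.5 sizes the trial for an MCPMod test at one-sided family-wise alpha 0.10, with 285 evaluable patients split 95:38:38:38:76. The maximum standardised effect is 0.32, "which is based on a mean difference between placebo and BI 1358894 of 3.0 and standard deviation of 9.5 for the primary endpoint". The section points to the pre-specified models of 7.2.2.1 and adds: "The powers for each model shape under different assumptions are summarized in the table below".

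Table 7.2.2.1:1 has five models: Emax1, Emax2, Sigmax, Exponential and Linear. Emax2 is the steep low-dose case, in which "70% of the maximum effect is achieved at 5 mg". Proof of concept is declared if at least one model contrast is significant.

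In the SAP (7.4.1, MCPMod Analysis), "the optimal contrasts corresponding to the candidate models are calculated as in the trial design stage", and Table 7.4.1:1 lists five sets of coefficients, Emax2 among them. Both documents thus describe one test with five contrasts.

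Under Assumption A, Table 7.5:1 gives Linear 81.9%, Emax1 81.7%, Emax2 75.2%, Sigmax 85.4%, Exponential 81.0%, average 81.1%.

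**The concern.** When a candidate shape has its own optimal contrast in the test, power under that shape is usually close to power under the others, because the maximum effect is the same. An Emax2 figure 6 to 10 points below the rest suggests that its contrast was not in the calculation.

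Two things depend on this. First, the table is the plan's only statement of how the design performs for each dose-response shape, so a reader would take a steep low-dose response to be the weak spot. Second, the critical value depends on which contrasts are tested. A slip in the design code should be ruled out in the analysis code as well.

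**Working it through.** **Inputs.** Protocol 7.5: n = 95, 38, 38, 38, 76 (total 285, so 285 − 5 = 280 degrees of freedom); SD 9.5; maximum difference 3.0, 3.3, 3.6 (Assumptions A, B, C); one-sided alpha 0.10. Protocol 7.2.2.1: doses 0, 5, 25, 75, 125 mg and the five shapes. SAP 7.4.1: contrasts weighted by group size.

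**1. Shapes.**
- Emax1: ED50 = 25.
- Emax2: 5/(5 + ED50) = 0.7, so ED50 = 5 × 0.3/0.7 = 2.143.
- Sigmax: ED50 = 25 and 3^h/(3^h + 1) = 0.9, so 3^h = 9 and h = 2.
- Exponential: (e^(25/δ) − 1)/(e^(125/δ) − 1) = 0.05, so δ = 45.41.
- Linear: no parameter.

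**2. Contrasts (reproducing the SAP).** The optimal coefficient is c_i ∝ n_i(f_i − f̄), with f̄ the n-weighted mean, scaled to unit length. For Emax2, f = 0, 0.7, 0.9211, 0.9722, 0.9831 and f̄ = 0.6079. The result is −0.8615, 0.0522, 0.1775, 0.2065, 0.4254. SAP Table 7.4.1:1 has −0.862, 0.052, 0.177, 0.206, 0.425. All 25 coefficients in that table agree to three decimals, so shapes, doses, weights and allocation are the sponsor's.

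**3. A check by hand.** The five-contrast critical value (multivariate t, 280 df) is 1.618. Power under Emax2 cannot be less than the power of the Emax2 contrast alone against that value. Its non-centrality is λ = (Δ/f_125) × √Σn_i(f_i − f̄)² / SD. With Σn_i(f_i − f̄)² = 54.90:

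λ = (3.0/0.9831) × 7.41 / 9.5 = 2.380, and Φ(2.380 − 1.618) = Φ(0.762) = 77.7%.

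Under B and C, λ = 2.618 and 2.856, giving 84.1% and 89.2%. The stated Emax2 powers are 75.2%, 82.7% and 86.6%. Each lies below this floor, so none can belong to the five-contrast test.

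**4. Full power.** Power = P(largest contrast t statistic > critical value), simulated with millions of draws. Simulation error is below 0.1 point.

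| Shape | A stated | A five contrasts | A without Emax2 contrast | B stated | B five | C stated | C five |
|---|---|---|---|---|---|---|---|
| Linear | 81.9 | 80.2 | 82.0 | 86.7 | 85.7 | 91.6 | 90.0 |
| Emax1 | 81.7 | 81.9 | 82.1 | 87.7 | 87.2 | 91.6 | 91.2 |
| Emax2 | 75.2 | 81.8 | 75.9 | 82.7 | 87.3 | 86.6 | 91.4 |
| Sigmax | 85.4 | 83.8 | 84.9 | 89.1 | 88.9 | 93.7 | 92.6 |
| Exponential | 81.0 | 78.8 | 81.0 | 85.8 | 84.5 | 90.5 | 89.1 |
| Average | 81.1 | 81.3 | 81.2 | 86.4 | 86.7 | 90.8 | 90.9 |

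Emax2 is understated by 81.8 − 75.2 = 6.6, 87.3 − 82.7 = 4.6 and 91.4 − 86.6 = 4.8 points. Under A, Exponential is overstated by 2.2, Linear by 1.7 and Sigmax by 1.6.

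**5. What the table does describe.** Testing only Linear, Emax1, Sigmax and Exponential (critical value 1.51) matches all 15 model-by-assumption cells within about 0.8 points. Among all subsets of the five contrasts, the four closest fits under Assumption A all omit Emax2. Other allocations, the randomised total of 355, equal-weight contrasts, a log-linear shape in place of linear, an asymptotic maximum effect, a normal critical value and alpha 0.05 do not reproduce the table.

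**6. Effect on the error rate if carried over.** Five contrasts tested against 1.51 instead of 1.62 would have a family-wise error of 12.1%, not 10%.

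**The case against.** The per-model rows drive no decision. The protocol's claim is about 81% average power, which holds, and it sets no 80% floor for a single model. The largest error is on the safe side: power under Emax2 is better than stated. The other discrepancies are small. Linear and Sigmax are off by less than 2 points under A, and Sigmax under B by only 0.2. With the effect size taken literally as 0.32 rather than 3.0/9.5 = 0.316, the five-contrast powers are 81.0, 82.7, 82.7, 84.6 and 79.7, so Exponential is then only 1.3 points off. The four-contrast explanation is not unique: a three-contrast set (Emax1, Sigmax, Exponential) fits about as well. Finally, nothing in the SAP suggests a wrong critical value. It lists five contrasts and requires family-wise control at 0.10.

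Most of this limits the consequence without removing the error. The Emax2 row is outside any rounding or simulation explanation, and every close fit lacks the Emax2 contrast. Exponential stays below 80% and is the weakest shape under either reading of the effect size. It is right that exactly which contrasts were used is an inference, since the R code is not in the public text. The 12.1% figure shows what a carried-over slip would cost; there is no evidence that it occurred.

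**Conclusion.** The table is wrong as written. For the test that the protocol and SAP define, power under Emax2 is about 82%, 87% and 91% (A, B, C), not 75.2%, 82.7% and 86.6%. Under Assumption A, Exponential is 78.8% (79.7% at a literal 0.32), not 81.0%, and it is the weakest case in place of Emax2. Linear and Sigmax are slightly overstated; Emax1 and the average reproduce. The conclusion rests on the stated SD, differences, allocation and shapes, and on group-size-weighted contrasts, which the SAP coefficients confirm. The omission of the Emax2 contrast is the likely cause but is inferred from the numbers. The sample size is unaffected.

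**What to change.** Re-run the power calculation (powMCT in DoseFinding) with all five contrasts and replace the rows of Table 7.5:1 with values of about:

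- A: Linear 80.2, Emax1 81.9, Emax2 81.8, Sigmax 83.8, Exponential 78.8; average 81.3
- B: 85.7, 87.2, 87.3, 88.9, 84.5; average 86.7
- C: 90.0, 91.2, 91.4, 92.6, 89.1; average 90.9

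State beneath the table which contrasts enter the test and the resulting critical value (about 1.62). Before unblinding, confirm that the MCPMod analysis code passes all five contrasts to the critical-value calculation.

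The cost is one restated table and one code check. Some single-model figures become slightly less favourable. The number of patients, the alpha level and the decision rule do not change.

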## **8. INFORMED CONSENT, TRIAL RECORDS, DATA PROTECTION, PUBLICATION POLICY, AND ADMINISTRATIVE STRUCTURE**

The trial will be carried out in compliance with the protocol, the ethical principles laid down in the Declaration of Helsinki, in accordance with the ICH Harmonized Guideline for Good Clinical Practice (GCP), relevant BI Standard Operating Procedures (SOPs), the EU directive 2001/20/EC, the EU directive 2001/20/EC / EU regulation 536/2014, the Japanese GCP regulations (Ministry of Health and Welfare Ordinance No. 28, March 27, 1997) and other relevant regulations. Investigators and site staff must adhere to these principles. Deviation from the protocol, the principles of ICH GCP or applicable regulations as will be treated as “protocol deviation”.

Standard medical care (prophylactic, diagnostic and therapeutic procedures) remains the responsibility of the treating physician of the patient.

The investigator will inform the sponsor immediately of any urgent safety measures taken to protect the trial patients against any immediate hazard, as well as of any serious breaches of the protocol or of ICH GCP.

The Boehringer Ingelheim transparency and publication policy can be found on the following web page: [trials.boehringer-ingelheim.com](https://trials.boehringer-ingelheim.com). The rights of the investigator and of the sponsor with regard to publication of the results of this trial are described in the investigator contract. As a rule, no trial results should be published prior to finalization of the Clinical Trial Report.

The certificate of insurance cover, if required locally, is made available to the investigator and the patients, and is stored in the ISF.

### **8.1 TRIAL APPROVAL, PATIENT INFORMATION, INFORMED CONSENT**

This trial will be initiated only after all required legal documentation has been reviewed and approved by the respective Institutional Review Board (IRB / Independent Ethics Committee (IEC and competent authority (CA) according to national and international regulations. The same applies for the implementation of changes introduced by amendments.

Prior to patient participation in the trial, written informed consent must be obtained from each patient (or the patient’s legally accepted representative) according to ICH-GCP and to the regulatory and legal requirements of the participating country. Each signature must be personally dated by each signatory and the informed consent and any additional patient-information form retained by the investigator as part of the trial records. A signed copy of the informed consent and any additional patient information must be given to each patient or the patient’s legally accepted representative.

The investigator or delegate must give a full explanation to trial patients based on the patient information form. A language understandable to the patient should be chosen, technical terms and expressions avoided, if possible.

The patient must be given sufficient time to consider participation in the trial. The investigator or delegate obtains written consent of the patient’s own free will with the

informed consent form after confirming that the patient understands the contents. The investigator or his delegate must sign (or place a seal on) and date the informed consent form. If a trial collaborator has given a supplementary explanation, the trial collaborator also signs (or places a seal on) and dates the informed consent.

Re-consenting may become necessary when new relevant information becomes available and should be conducted according to the sponsor's instructions.

If study conduct needs to be adjusted (see sections [4.1.4](#), [6.2](#) and [10.3](#)) during the COVID-19 pandemic, patients must be made aware of any modifications and their consent needs to be obtained prior to implementation.

The consent and re-consenting process should be properly documented in the source documentation.

